6.3. Data Handling Convention for Efficacy Variables

Algorithm for calculation of Area Under the Curve (AUC):

The AUC for titrated SPT will be calculated using the trapezoidal rule. The AUC will be calculated using the formula:

$$AUC = \left[\sum_{i=1}^{4} (c_i - c_{i-1}) * (D_i + D_{i-1})/2\right] / (c_4 - c_0)$$

where

- D_i is the normalized mean wheal at concentration c_i
- c_i is the concentration for which D_i is measured, $c_0 = \frac{1}{20,000}$, $c_1 = \frac{1}{2,000}$, $c_2 = \frac{1}{200}$, $c_3 = \frac{1}{20}$, $c_4 = 1$.

6.4. Data Handling Convention for Missing Data

Missing data will not be imputed in listings. This section includes the methods for missing data imputation for some summary analyses, if necessary.

Protocol: R668-ALG-1702

Date: March 3, 2021

Rules for handling missing data for primary and secondary efficacy variables are described in Section 4.5.1 and Section 4.5.2.

Adverse event

If the intensity of a TEAE is missing, it will be classified as "severe" in the frequency tables by intensity of TEAEs. If the assessment of relationship of a TEAE to the investigational product is missing, it will be classified as related to the investigational product.

Adverse event start date

AE start date will be used for AE classification and analysis of AESIs. If AE start date is not complete, then the character variable will keep the original incomplete date, the numerical date variable will be imputed, and an imputation flag will be indicate which date component is missing.

If AE start day is missing, and AE start month and year are not missing: If AE start year is the same as first dose year and AE start month is the same as first dose month, then AE start day will be imputed using the day of first dose. If this leads to a date after the AE end date, AE end date will be used instead. If AE start year is the same as first dose year and AE start month different from first dose month, AE start day will be imputed using the first day of the month. If this leads to a date before informed consent date, the informed consent date will be used. Imputation flag is 'D'.

If AE start month is missing, and AE start year is not missing: If AE start year is before the first dose year, the informed consent day and month will be used. If AE start year is the same as first dose year, the first dose day and month will be used. If this leads to a date after AE end date, AE end date will be used instead. If AE start year is after the first dose year, January 1st will be used. Imputation flag is 'M'.

If AE start year is missing: The date of first dose will be used. If this leads to a date after the AE end date, AE end date will be used instead. Imputation flag is 'Y'.

Adverse event end date

The general recommendation is not to impute AE end date. However, since AE end date will be used for AE start date imputation, to carry through the logic for programming, the following intermediate step will be used. Afterwards, only the original character/numeric date recorded in CRF will be kept in the final analysis dataset.

If AE end day is missing, and AE end month and year are not missing: AE end date will be imputed using the last day of the month. If this leads to a date after end of study follow up date, the end of follow up date will be used instead.

If AE end month is missing, and AE end year is not missing: AE end date will be imputed using December 31st as the day and month. If this leads to a date after end of study follow up date, the end of follow up date will be used instead.

If AE end year is missing: AE end date will be imputed using end of follow up date.

Prior or concomitant medication

Medication start and end date missing

To determine whether a medication is prior medication or concomitant medication or both, the missing medication start date is estimated as early as possible, and the missing medication end date is estimated as late as possible. If the medication start date is missing, the onset day will not be calculated in medication listing.

Protocol: R668-ALG-1702

Date: March 3, 2021

Prior medication start date

If start day is missing, and start month and year are not missing: the start day will be imputed using the first day of the month. Imputation flag is 'D'.

If start month is missing, and start year is not missing: the day and month will be imputed using January 1st. Imputation flag is 'M'.

If start year is missing: the start date will be imputed using 2 years before informed consent date. Imputation flag is 'Y'.

A special note: for start date with year missing, the general principle is not to impute. However, to simplify the programming flow, the imputation is proposed to align with protocol which specifices to collect up to 2 years prior medication. Since the start date of prior medication will not be used in any analysis, the rule will not impact the analysis result.

Prior medication end date

If end day is missing, and end month and year are not missing: the end date will be imputed using the last day of the month. If this leads to a date on or after first dose intake date, the first dose intake date -1 will be used. Imputation flag is 'D'.

If end month is missing, and end year is not missing: the end date will be imputed using December 31^{st} as the day and month. If this leads to a date on or after first dose intake date, the first dose intake date – 1 will be used instead. Imputation flag is 'M'.

If end year is missing: the end date will be imputed using the first dose intake date -1. Imputation flag is 'Y'.

Concomitant medication start date

The imputation rule for concomitant medication start date is the same as AE start date.

Concomitant medication end date

If end day is missing, and end month and year are not missing: the end date will be imputed using the last day of the month. If this leads to a date after end of study follow up date, the end of follow up date will be used. Imputation flag is 'D'.

If end month is missing, and end year is not missing: the end date will be imputed using December 31st as the day and month. If this leads to a date after end of study follow up date, the end of follow up date will be used instead. Imputation flag is 'M'.

If end year is missing: the end date will be imputed using the end of follow up date. Imputation flag is 'Y'.

Medication coding

Medications whose ATC level 4 cannot be coded will be summarized by setting ATC4=ATC 2 in the table programs. However, these uncoded ATC level 4 records still need to be confirmed with study DM and study MD.

Protocol: R668-ALG-1702

Date: March 3, 2021

PCSV

Patients who had post-baseline PCSV but missing baseline value will be regarded as having treatment-emergent PCSV.

6.5. Visit Windows

Data analyzed by-visit-analysis (including efficacy, laboratory data, vital sign and spirometry/PEF) will be summarized by the study scheduled visits described in the study protocol and SAP, "Schedule of Event". The analysis visit windows will be exhaustive so that all available values obtained from unscheduled visits and early termination (ET) visit have the potential to be summarized. No analysis visit windows will be applied for the study scheduled visits.

The following analysis visit windows will be used to map the unscheduled visits and ET visits, based on the study day:

Visit	Target Day (TD)	Analysis Time Window Based on Study Day*
Screening 1	-57 to -43	-57 to -43
Screening 1a	-42 to -15	-42 to -15
Baseline	1	1
Visit 3 (Week 2)	15	[2, 22]
Visit 4 (Week 4)	29	[23, 36]
Visit 5 (Week 6)	43	[37, 50]
Visit 6 (Week 8)	57	[51, 64]
Visit 7 (Week 10)	71	[65, 78]
Visit 8 (Week 12)	85	[79, 92]
Visit 9 (Week 14)	99	[93, 106]
Visit 10 (Week 16)	113	[107, 120]
Visit 11 (Week 18)	127	[121, 134]
Visit 12 (Week 20)	141	[135, 148]
Visit 13 (Week 22)	155	[149, 162]
Visit 14 (Week 24)	169	[163, 176]
Visit 15 (Week 30)	211	[177, 232]
Visit 16 (Week 36)	253	≥233

^{*}Study day is calculated relative to the date of first study drug injection

In general, the following order will be used to select the record for analysis at give visit:

- 1. Scheduled visit
- 2. Early termination (ET) or end of study (EOS), whichever comes first if scheduled visit is not available

Protocol: R668-ALG-1702

Date: March 3, 2021

3. Unscheduled visit if both scheduled visit and ET/EOT/EOS are not available

For multiple measurements of the same test in the same window, the following rules will be used to select the analysis value:

- If multiple valid values of a variable within an analysis visit window, the closest from the target study day will be selected.
- If the difference is a tie, the value after the target study day will be used.
- If multiple available values of a variable exist within a same day, then the first value of the day will be selected.

7. INTERIM ANALYSIS

No interim analysis is planned.

Data may be analyzed and reviewed internally by the sponsors.

A primary analysis may be performed once all patients in the study have completed the 24-week treatment period (week 24 visit or earlier for those patients who are withdrawn prematurely from the study). If performed, this primary analysis will be considered as the final analysis for the primary endpoint and secondary efficacy endpoints up to week 24.

Protocol: R668-ALG-1702

10. APPENDIX

10.1. Summary of Statistical Analyses

Efficacy Analysis:

Endpoint	Analysis Populations	Primary Statistical Method	Supportive/Sensitivity Analysis	Subgroup Analysis	Other Analyses
Primary Endpoint					•
Proportion of patients treated with dupilumab that pass a DBPCFC with at least 444 mg (cumulative) peanut protein at week 24	SAF	Descriptive statistics/missing data as non-responder	Descriptive statistics with available week 24 data	Yes	Bar chart
Secondary Endpoints					
Change in the cumulative tolerated dose (log transformed) mg of peanut protein during a DBPCFC from baseline to measured DBPCFC visits at week 24	SAF	Descriptive statistics/LOCF method	Descriptive statistics with available week 24 data	Yes	Bar chart
Change in the cumulative tolerated dose (log transformed) mg of peanut protein during a DBPCFC from baseline to measured DBPCFC visits at week 36	Subset of SAF at week 36	Descriptive statistics	No	No	Bar chart
Proportion of patients treated with dupilumab that pass a DBPCFC with at least 444 mg (cumulative) peanut protein at week 36	Subset of SAF at week 36	Descriptive statistics	No	No	Bar chart
Proportion of patients treated with dupilumab that pass a DBPCFC with at least 1044 mg (cumulative) peanut protein at week 24	SAF	Descriptive statistics/missing data as non-responder	No	Yes	Bar chart

Endpoint	Analysis Populations	Primary Statistical Method	Supportive/Sensitivity Analysis	Subgroup Analysis	Other Analyses
Proportion of patients treated with dupilumab that pass a DBPCFC with at least 1044 mg (cumulative) peanut protein at week 36	Subset of SAF at week 36	Descriptive statistics	No	No	Bar chart
Proportion of patients treated with dupilumab that pass a DBPCFC with 2044 mg (cumulative) peanut protein at week 24	SAF	Descriptive statistics/missing data as non-responder	No	Yes	Bar chart
Proportion of patients treated with dupilumab that pass a DBPCFC with 2044 mg (cumulative) peanut protein at week 36	Subset of SAF at week 36	Descriptive statistics	No	No	Bar chart

Safety Analysis:

Endpoint	Analysis Populations	Primary Statistical Method	Supportive/Sensitivity Analysis	Subgroup Analysis	Other Analyses
Primary Endpoint					
Adverse events	SAF	Descriptive Statistics and time-to- event analysis	No	Yes, for selected AE summary	No
Laboratory measures	SAF	Desriptive Statistics	No	No	No
Vital sign	SAF	Descriptive Statistics	No	No	No
Spirometry	SAF	Descriptive Statistics	No	No	No

10.2. Schedule of Time and Events

 Table 1
 Schedule of Events

Study Procedure	Scre	ening						Tre	atme	nt Pei	riod					Follo	ow-up	UV	ET
Visit	V1	Vla	V2 Baseline	V3 phone	V4 clinic	V5 phone	V6 clinic	V7 phone	V8 clinic	V9 phone	V10 clinic	V11 phone	V12 clinic	V13 phone	EOT V14 clinic	V15	EOS V16	if app	licable
Day	-57 to -43	-42 to -15	1	15	29	43	57	71	85	99	113	127	141	155	169	211	253		
Week				2	4	6	8	10	12	14	16	18	20	22	24	30	36		
Visit Window (days)				±3	±3	±3	±3	±3	±3	±3	±3	±3	±3	±3	±3	±3	±3		
Screening/Baseline:																			
Inclusion/Exclusion	X		X																
Informed Consent/Assent	X																		
Medical History	X																		
Demographics	X																		
Enrollment			X																
Epi injection training			X																
Training on Study Drug Administration			X																
Treatment:																			
Administer Study Drug ¹			X	X	X	X	X	X	X	X	X	X	X	X					
Study Drug Dispensation/Account			X		X		X		X		X		X		X				
Phone call to collect AEs, Conmeds and IP compliance				X		X		X		X		X		X					
Concomitant Meds and Tx	X	X	X		X		X		X		X		X		X	X	X	X	X
Efficacy ⁵ :																			
DBPCFC ^{2, 3,4}		X													X		X^{10}		
Peanut SPT ³	X																		
Titrated Peanut SPT ^{3,7}			X		X				X						X		X		X
FAQLQ			X						X						X		X		

Study Procedure	Scre	ening						Tre	atme	nt Pei	riod					Follo	ow-up	UV	ET
Visit	V1	Vla	V2 Baseline	V3 phone	V4 clinic	V5 phone	V6 clinic	V7 phone	V8 clinic	V9 phone	V10 clinic	V11 phone	V12 clinic	V13 phone	EOT V14 clinic	V15	EOS V16	if app	licable
Day	-57 to -43	-42 to -15	1	15	29	43	57	71	85	99	113	127	141	155	169	211	253		
Week				2	4	6	8	10	12	14	16	18	20	22	24	30	36		
Visit Window (days)				±3	±3	±3	±3	±3	±3	±3	±3	±3	±3	±3	±3	±3	±3		
Safety:		T	1								1			1	ı	,			
Weight ⁵	X		X		X		X		X		X		X		X	X	X	X	X
Height ⁵	X																		
Vital Signs ⁵	X	X	X		X		X		X		X		X		X	X	X	X	X
Physical Examination ⁵	X	X							X						X		X		X
Spirometry ⁶	X	X							X						X		X		X
Adverse Events ⁵	X	X	X		X		X		X		X		X		X	X	X	X	X
Laboratory Testing:																			
HIV Ab, HBsAg, HBcAb, Hep C Ab ⁵	X																		
Hematology/Chemistry ⁵	X		X						X						X		X	X	X
FeNO Test ⁶		X							X						X		X		X
Pregnancy Test (WOCBP) ⁵	S	U	U		U		U		U		U		U		U	U	S		U
Urinalysis ⁵	X	X	X						X						X		X	X	X
Total IgE ⁵			X						X						X		X		X
Peanut sIgE, sIgG, and sIgG4 ⁵	X		X		X		X		X		X				X	X	X		X
Research Samples (serum/plasma) ⁵		X	X						X						X		X		X
Blood samples for additional exploratory ⁵ research ⁷			X						X						X		X		X

Study Procedure	Scre	ening						Tre	atme	nt Pei	riod					Follo	ow-up	UV	ET
Visit	V1	V1a	V2 Baseline	V3 phone	V4 clinic	V5 phone	V6 clinic	V7 phone	V8 clinic	V9 phone	V10 clinic	V11 phone	V12 clinic	V13 phone	EOT V14 clinic	V15	EOS V16	if app	licable
Day	-57 to -43	-42 to -15	1	15	29	43	57	71	85	99	113	127	141	155	169	211	253		
Week				2	4	6	8	10	12	14	16	18	20	22	24	30	36		
Visit Window (days)				±3	±3	±3	±3	±3	±3	±3	±3	±3	±3	±3	±3	±3	±3		
PK/Drug Concentration and ADA Samples ⁸ :																			
PK/Drug conc. sample			X				X		X						X		X		X
ADA sample			X						X						X		X		X
Genomic DNA sample9:																			
Buccal swab samples for			X																

Date: March 3, 2021

WOCBP = women of childbearing potential

DNA

Footnotes for the Schedule of Events Table

- 1. Study drug will be administered in the clinic on day 1 by the study team, patient's caregiver, or patient. With adequate training, study drug may be administered at home Q2W for the remaining injections. Patient/caregiver will complete an injection log to document compliance with injection of study drug and to document any AEs and concomitant medications.
- 2. During DBPCFC, vital signs will be collected every 15 to 30 minutes. After initial DBPCFC dose, only pulse and blood pressure need to be taken as part of safety monitoring.
- 3. Patients should not take antihistamines within 5 days prior to SPTs and day 1 of the DBPCFCs.
- 4. The food challenges (DBPCFC) will be performed on different days (1 day placebo [oat] protein, 1 day peanut protein, with order determined at random) at least 24 hours, but no more than 7 days, apart and not within 24 hours of a dose of study drug. After the last dose of the DBPCFC, the patient will be monitored for at least 2 hours and then discharged from the clinic.
- 5. Assessments will be performed before the administration of study drug.

Regeneron Pharmaceuticals, Inc. Statistical Analysis Plan

Protocol: R668-ALG-1702 Date: March 3, 2021

- 6. FeNO measurement and spirometry will be performed on the same day, except for visit 1, in which only spirometry is performed. If the DBPCFC is scheduled on the day of the visit, then both FeNO measurement and spirometry will be performed twice before the patient goes home: once before DBPCFC, once after DBPCFC. FeNO should be done prior to spirometry.
- 7. On the day of the DBPCFCs, blood draws for exploratory research, including TruCulture, basophil sensitivity, and peripheral blood mononuclear cells (PBMC) samples will be performed before the DBPCFC is performed. On the day of the DBPCFC, titrated SPTs will be performed before the DBPCFC.
- 8. Samples for PK and ADA analysis should be collected prior to drug administration.
- 9. Two buccal swabs for genomic analysis can be collected on day 1 or any day after day 1.
- 10. Only patients who passed a DBPCFC of at least 444 mg (cumulative) at week 24 will undergo a final DBPCFC (up to 2044 mg cumulative).

10.3. Criteria for Potentially Clinically Significant Values (PCSV)

Protocol: R668-ALG-1702 Date: March 3, 2021

Parameter	Treatment Emergent PCSV	Comments
Clinical Chemistry		
Alanine Aminotransferas e	>3 and ≤ 5 ULN and baseline ≤ 3 ULN >5 and ≤ 10 ULN and baseline ≤ 5 ULN	Enzyme activity must be expressed in ULN, not in IU/L. Concept paper on DILI – FDA draft Guidance
(ALT)	>10 and ≤ 20 ULN and baseline ≤ 10 ULN >20 ULN and baseline ≤ 20 ULN	Oct 2007. Each category is calculated independently.
Aspartate Aminotransferas e	>3 and ≤ 5 ULN and baseline ≤ 3 ULN >5 and ≤ 10 ULN and baseline ≤ 5 ULN	Enzyme activity must be expressed in ULN, not in IU/L.
(AST)	>10 and ≤ 20 ULN and baseline ≤ 10 ULN	Concept paper on DILI – FDA draft Guidance Oct 2007.
	>20 ULN and baseline ≤ 20 ULN	Each category is calculated independently.
Alkaline Phosphatase	>1.5 ULN and baseline ≤ 1.5 ULN	Enzyme activity must be expressed in ULN, not in IU/L.
(ALP)		Concept paper on DILI – FDA draft Guidance Oct 2007.
Bilirubin (BILI)	>1.3 ULN and baseline ≤ 1.3 ULN	Must be expressed in ULN, not in μmol/L or mg/L.
		Based on normal range: <1 mg/dL, CF = mg x $1.7 = \mu$ mol
		Concept paper on DILI – FDA draft Guidance Oct 2007.
		Based on normal ranges: <6 mg/dL (Term 0-1 day), <8 mg/dL (Term 1-2 days), <12 mg/dL (Term 3-5 days), <1 mg/dL (Term >5 days)
Conjugated Bilirubin	(Direct Bilirubin >35% Total Bilirubin and Total Bilirubin >1.3 ULN) and (Direct Bilirubin ≤35% Total Bilirubin or Total	Conjugated bilirubin will be measured when the total Bilirubin is above the ULN
	Bilirubin ≤1.3 ULN) at baseline	Based on normal range: 0 to 0.4 mg/dL
(ALT or AST) and Bilirubin (BILI)	((ALT > 3 ULN or AST >3 ULN)) and BILI >2 ULN) and baseline ((ALT ≤3 ULN and AST ≤3 ULN) or BILI ≤2 ULN)	Concept paper on DILI – FDA draft Guidance Oct 2007.
Creatine Kinase (CK)	>5 ULN and ≤10 ULN and baseline ≤5 ULN >10 ULN and baseline ≤10 ULN	

Parameter	Treatment Emergent PCSV	Comments
Creatinine (CREAT)	>=30% increase from individual patient baseline	
	>=60% increase from individual patient baseline	
Urate (URATE) Hyperuricemia	>=30% increase from individual patient baseline	
Hypouricemia	>=60% increase from individual patient baseline	
Urea Nitrogen (UREAN)	>=30% increase from individual patient baseline	
	>=60% increase from individual patient baseline	
Chloride (CL) Hypochloremia Hyperchloremia	<80 mmol/L and baseline ≥ 80 mmol/L >115 mmol/L and baseline ≤ 115 mmol/L	Two independent criteria
Sodium (SODIUM)	<129 mmol/L and baseline ≥129 mmol/L	Two independent criteria
Hyponatremia Hypernatremia	>150 mmol/L and baseline ≤ 150 mmol/L	
Potassium (K) Hypokalemia Hyperkalemia	<3.5 mmol/L and baseline ≥ 3.5 mmol/L >5.0 mmol/L and baseline ≤ 5.0 mmol/L	Two independent criteria
Cholesterol (Cholesterol)	>6.20 mmol/L and ≤ 6.20 mmol/L at baseline	
Triglycerides (TRIG)	> 5.64 mmol/L and ≤ 5.64 mmol/L at baseline	Threshold for therapeutic intervention with pharmacotherapy in children. (Expert Panel on Integrated Guidelines for Cardiovascular Health and Risk Reduction in Children and Adolescents; 2011).
		$CF = g \times 1.14 = mmol$
Glucose (GLUC)	≤ 2.7 mmol/L	
Hypoglycaemia Hyperglycaemia	≥10 mmol/L	
Albumin (ALB)	<25 g/L and ≥25 g/L at baseline	
Calcium (CA)	<2 mmol/L and baseline ≥2 mmol/L	
	>2.9 mmol/L and baseline ≤2.9 mmol/L	

Parameter	Treatment Emergent PCSV	Comments
LDL Cholesterol (LDL)	>4.91 mmol/L and ≤4.91 mmol/L at baseline	Threshold for therapeutic intervention with pharmacotherapy in children (Expert Panel on Integrated Guidelines for Cardiovascular Health and Risk Reduction in Children and Adolescents; 2011).
Hematology		
Leukocytes	<4.0 Giga/L and ≥4.0 Giga/L at baseline	
(WBC)	>13.5 Giga/L and ≤13.5 Giga/L at baseline	
Lymphocytes	<0.6 Giga/L and ≥0.6 Giga/L at baseline	
(LYM)	>6.0 Giga/L and ≤6.0 Giga/L at baseline	
Neutrophils	<1.2 Giga/L and ≥1.2 Giga/L at baseline	
(NEUT)	>ULN and baseline ≤ ULN	
Monocytes (MONO)	>1.2 Giga/L and ≤ 1.2 Giga/L at baseline	
Basophils (BASO)	>0.2 Giga/L	
Eosinophils (EOS)	(>0.5 Giga/L and >ULN) and (≤ 0.5 Giga/L or ≤ ULN at baseline)	Harrison- Principles of internal Medicine 17th Ed., 2008.
Hemoglobin (HGB)	<100 g/L and ≥100 g/L at baseline or any decrease ≥ 20 g/L	Two criteria are independent
	>200 g/L and ≤200 g/L at baseline	
Hematocrit (HCT)	$<0.37 \text{ v/v}$ and $\geq 0.37 \text{ v/v}$ at baseline for Male;	Two criteria are independent
	<0.33 v/v and ≥0.33 v/v at baseline for Female	
	>0.52 v/v and ≤0.52 v/v at baseline for Male; >0.47 v/v and ≤0.47 v/v at baseline for	
Di e i e	Female	
Platelets (PLAT)	<100 Giga/L and ≥100 Giga/L at baseline	International Consensus meeting on drug- induced blood cytopenias, 1991.
	>700 Giga/L and ≤700 Giga/L at baseline	Two independent criteria
Urinalysis		-
pH (PH)	<5 or >8	
Ketones (KETONES)	Presence and absence at baseline	Semi-quantitative methods
Ketonuria		

Parameter	Treatment Emergent PCSV	Comments
Glucose (GLUC)	Presence and absence at baseline	Semi-quantitative methods
Glycosuria		
Erythrocytes (RBC)	> 5 RBCs/ HPF and ≤5 RBCs/ HPF at baseline	Semi-quantitative methods
Microscopic Hematuria		
Protein (PROT) Proteinuria	≥ 1+ and <1+ at baseline	Semi-quantitative methods, ≥ 1+ means concentration ≥30 mg/dL
Vital Signs		
HR	≤50 bpm and decrease from baseline ≥20 bpm ≥120 bpm and increase from baseline ≥20 bpm	To be applied for all positions (including missing) except STANDING.
SBP	≤90 mmHg and decrease from baseline ≥20 mmHg ≥119 mmHg and increase from baseline ≥20 mmHg.	
DBP	≤54 mmHg and decrease from baseline ≥10 mmHg ≥78 mmHg and increase from baseline ≥10 mmHg	
Temperature	Rectal, Tympanic: >100.4 °F/38.0 °C Oral: >99.5 °F/37.5 °C Axillary or skin infrared (temporal): >99 °F/37.2 °C	
Respiratory rate	< 12 per minute and ≥12 per minute at baseline >20 per minute and ≤20 per minute at baseline	
Weight	≥5% weight loss from baseline	Based on identification of trends in the child's growth with a series of visits WHO Multicentre Reference Study Group, 2006; Center for Disease Control. Growth chart 2007.

10.4. Adverse Event of Special Interest (AESI)

10.4. Adverse Evei	nt of Special Interest (AESI)
AESI	Search Criteria
Anaphylactic reactions	SMQ narrow "Anaphylactic Reactions"
Systemic hypersensitivity reactions	Narrow SMQ for hypersensitivity Note: manual adjudication of relevant PTs will be required by the study medical monitor, before database lock
Malignancy	Malignant tumours (SMQ) [Broad or Narrow]
Helminthic infections	 HLT = Cestode infections HLT = Helminthic infections NEC HLT = Nematode infections HLT = Trematode infections
Suicidal behavior	Include the following PTs Completed suicide Suicidal ideation Suicide attempt Depression suicidal Suicidal behaviour Assisted Suicide
Any type of conjunctivitis or blepharitis (severe or serious)	Broad CMQ conjunctivitis PTs (Conjunctivitis, Conjunctivitis allergic, Conjunctivitis bacterial, Conjunctivitis viral, Atopic keratoconjunctivitis, Blepharitis, Dry eye, Eye irritation, Eye pruritus, Lacrimation increased, Eye discharge, Foreign body sensation in eyes, Photophobia, Ocular hyperaemia, Conjunctival hyperaemia, Xerophthalmia) Blepharitis PTs (Bacterial blepharitis, blepharitis allergic)
	AND
	Serious AE= "Yes" OR Severity= "severe"
Keratitis	CMQ Keratitis PTs:
	1. Allergic keratitis 2. Atopic keratoconjunctivitis 3. Diffuse lamellar
	keratitis 4. Exposure keratitis 5. Keratitis 6. Keratitis interstitial
	7. Keratitis sclerosing 8. Keratopathy 9. Keratorhexis 10.
	Keratouveitis 11. Neurotrophic keratopathy 12. Punctate keratitis 13.
	Superior limbic keratoconjunctivitis 14. Ulcerative keratitis 15. Vernal
	keratoconjunctivitis 16. Acanthamoeba keratitis 17. Infectious
	crystalline keratopathy 18. Infective Keratitis 19. Keratitis bacterial
	20. Keratitis fungal 21. Keratitis viral 22. Keratoconjunctivitis measles

[figure not shown]
Protocol: R668-ALG-1702

AESI	Search Criteria
	23. Varicella keratitis 24. Viral keratouveitis 25.Corneal
	neovascularization 26. Limbal swelling 27. Corneal abrasion 28.
	Corneal abscess 29. Corneal bleeding 30. Corneal defect 31. Corneal
	disorder 32. Corneal epithelium defect 33. Corneal erosion 34.
	Corneal infection 35. Corneal irritation 36. Corneal lesion 37. Corneal
	leukoma 38. Corneal opacity 39. Corneal perforation 40. Corneal scar
	41. Infective corneal ulcer 42. Injury corneal 43. Limbal stem cell
	deficiency

Date: March 3, 2021

The search criteria are meant to assist the process of identification of TEAE of Special Interest/TEAE Syndrome. However, since these criteria might not be exhaustive in some cases or may not be specific in other cases. Hence an additional blinded review of all PTs in the database may be performed by the Medical monitor, based on medical judgement, to identify any TEAE of Special Interest/TEAE Syndrome that might have been missed by the criteria or to identify any TEAE may been inaccurately assigned as AESI by the algorithmic search

Signature Page for VV-RIM-00146253 v1.0

Signature Page for VV-RIM-00146253 v1.0 Approved

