10.4.3. Other Events that Require Accelerated Reporting to Sponsor

The following events also require reporting to the sponsor (or designee) within 24 hours of learning of the event:

Symptomatic Overdose of Study Drug: Dupilumab is administered every 14±3 days Q2W. The doses of this investigational product must be separated by ≥11 days to avoid overdose. Accidental or intentional overdose of at least 2 times the intended dose of study drug within the intended therapeutic window, if associated with an AE.

Pregnancy: Although pregnancy is not considered an AE, it is the responsibility of the investigator to report to the sponsor (or designee), within 24 hours of identification, any pregnancy occurring in a female during the study or within 12 weeks of the last dose of study drug. Any complication of pregnancy affecting a female study patient and/or fetus and/or newborn that meets the SAE criteria must be reported as an SAE. Outcome for all pregnancies should be reported to the sponsor.

Adverse Events of Special Interest: All AESI, serious and nonserious, must be reported within 24 hours of identification using the same reporting process as for SAE reporting, per Section 10.4.2. Adverse events of special interest for this study include the following:

- Anaphylactic reactions
- Systemic or extensive hypersensitivity reactions
- Malignancy
- Helminthic infections
- Suicide-related events
- Conjunctivitis (any type or etiology), keratitis or blepharitis (for all these AEs only events that are severe or serious or lasting ≥4 weeks will be reported as AESIs)

Refer to the study manual for the procedures to be followed.

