11.4.4. Safety Analysis

11.4.4.1. Adverse Events

Definitions

For safety variables, 2 observation periods are defined:

- The pretreatment period is defined as the time from signing the ICF to before the first dose of study drug.
- The treatment-emergent period is defined as the day from first dose of study drug to the end of the study. The treatment-emergent period includes the 24-week treatment period and follow-up period

Treatment-emergent adverse events are defined as those that are not present at baseline or represent the exacerbation of a pre-existing condition during the treatment-emergent period.

Analysis

All AEs reported in this study will be coded using the currently available version of the Medical Dictionary for Regulatory Activities (MedDRA[®]). Coding will be to lowest level terms. The verbatim text, the preferred term (PT), and the primary system organ class (SOC) will be listed.

Summaries of all TEAEs will include:

- The number (n) and percentage (%) of patients with at least 1 TEAE by SOC and PT
- TEAEs by severity (according to the grading scale outlined in Section 10.5.1), presented by SOC and PT
- TEAEs by relationship to treatment (related, not related), presented by SOC and PT
- Treatment-emergent AESIs (defined with a PT or a prespecified grouping)

Deaths and other SAEs will be listed and summarized.

Treatment-emergent adverse events leading to permanent treatment discontinuation will be listed and summarized.

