4.6.2. Adverse Events of Special Interest

Adverse events of special interest (AESI) for this study include the following:

- Anaphylactic reactions
- Systemic or extensive hypersensitivity reactions
- Malignancy
- Helminthic infections
- Suicide-related events
- Conjunctivitis (any type or etiology), keratitis or blepharitis (for all these AEs only events that are severe or serious or lasting ≥ 4 weeks will be reported as AESIs)

Section 10.4 provides a list of AESIs search criteria.

Anaphylaxis: is defined as a severe, potentially life-threatening systemic hypersensitivity reaction, characterized by being rapid in onset with life-threatening airway, breathing, or circulatory problems that is usually, though not always, associated with skin and mucosal changes.

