5.7.2. Analysis of Adverse Events of Special Interest

The adverse events of special interest (AESI) will be summarized by AESI category (see Section 10.4) and HLT/PT. In addition, it will be summarized by AESI category only.

Protocol: R668-ALG-1702

Date: March 3, 2021

The time to first AESIs (AESI by category) will be assessed by Kaplan-Meier estimates. Kaplan-Meier curves will be provided. The time is defined as the date of first event – date of first dose + 1. Patients without an event will be censored at the end of study visit.

The number of anaphylactic reactions, the number and percentage of patients experiencing an anaphylactic reaction, the number and percentage of patients experiencing an anaphylactic reaction by maximum severity using the Muraro Grading Scale (Muraro 2007), the number of patients experiencing an anaphylactic reaction was an SAE, the number of patients experiencing an anaphylactic reaction that required use of epinephrine will be summarized during DBPCFCs.

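### The SAP 10.4 search does not implement the SAP's own ocular AESI definition: the conjunctivitis/blepharitis row has no 4-week duration arm, and the keratitis row has no filter

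*SAP*

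**What the plan says.** SAP 4.6.2 gives one rule for conjunctivitis, keratitis and blepharitis together: "only events that are severe or serious or lasting ≥ 4 weeks will be reported as AESIs". Protocol 10.4.3 has the same rule: "only events that are severe or serious or lasting ≥4 weeks will be reported as AESIs". SAP 4.6.2 then points to the operational criteria ("Section 10.4 provides a list of AESIs search criteria"), and SAP 5.7.2 builds the tables on them: "The adverse events of special interest (AESI) will be summarized by AESI category (see Section 10.4) and HLT/PT". The Kaplan-Meier estimates of time to first AESI in SAP 5.7.2 are also by AESI category.

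SAP 10.4 treats the ocular events in two rows:

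- **Conjunctivitis/blepharitis.** The label is "Any type of conjunctivitis or blepharitis (severe or serious)". The row lists preferred terms and joins them with AND to the condition "Serious AE= 'Yes' OR Severity= 'severe". Duration appears in neither the label nor the condition.
- **Keratitis.** The row is a numbered list of preferred terms. It has no condition on seriousness, severity or duration.

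The text closing SAP 10.4 says that the criteria assist identification and may be neither exhaustive nor specific. It allows, but does not require, a further review of preferred terms by the medical monitor, who may add missed events or remove wrongly assigned ones.

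**The concern.** The definition and the search that is meant to carry it out are in the same document and disagree. A programmer working from SAP 4.6.2 and one working from SAP 10.4 could produce different AESI tables from the same data.

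The two mismatches run in opposite directions. In the conjunctivitis/blepharitis row, the events lost are the ones that the duration arm exists to catch: neither serious nor severe, but persistent. In the keratitis row, short mild or moderate events are added that the definition excludes.

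Conjunctivitis is one of the events that Protocol 3.3.1 reports at a higher rate on dupilumab than on placebo in adolescents with atopic dermatitis. Its AESI count is therefore one that readers of the study report are likely to look at.

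**Working it through.** No figure in the plan is at issue, so the check sets the rules side by side.

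**Inputs.** Definition: SAP 4.6.2 and Protocol 10.4.3. Search: SAP 10.4. The conjunctivitis/blepharitis row has 16 conjunctivitis-list terms + 2 blepharitis-list terms = 18. The keratitis row has terms numbered 1 to 43. One term, atopic keratoconjunctivitis, is on both lists.

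**Truth table.** Serious (yes/no), severe (yes/no) and lasting at least 4 weeks (yes/no) give 2 × 2 × 2 = 8 combinations. Three of the four serious/severe combinations have at least one yes.

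| Serious or severe | At least 4 weeks | Combinations | Definition | Conjunctivitis/blepharitis search | Keratitis search |
|---|---|---|---|---|---|
| Yes | Yes | 3 | In | In | In |
| Yes | No | 3 | In | In | In |
| No | Yes | 1 | In | **Out** | In |
| No | No | 1 | Out | Out | **In** |
| Total in | | 8 | 7 | 6 | 8 |

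**Reading the two differences.**

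- Conjunctivitis/blepharitis: 7 combinations qualify under the definition and 6 under the search. The missing one is non-serious, non-severe and at least 4 weeks long. This holds for 18 of 18 terms in that row. Such an event coded to atopic keratoconjunctivitis would still be counted under keratitis; for the other 17 terms it falls in neither ocular row.
- Keratitis: 7 combinations qualify under the definition and 8 under the search. The extra one is non-serious, non-severe and shorter than 4 weeks. This holds for 43 of 43 terms; a brief mild corneal abrasion is an example.

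**Is it a declared change?** SAP 1.2.3 lists two modifications from the protocol: the analysis sets, and the move from inferential to descriptive analysis. Neither concerns AESIs.

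**Can duration be used?** Yes. SAP 5.7.1 already lists AE start date, end date and duration as listing variables.

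**After the fix.** With serious OR severe OR at least 4 weeks applied to both rows, each search qualifies 7 of 8 combinations, the same 7 as the definition.

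**Size.** The documents give no durations for ocular events, so the number affected cannot be estimated. For scale only: if all of the approximately 24 planned patients are treated, one patient moved into or out of a category shifts its incidence by 1/24 = 4.2 percentage points.

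**The case against.** The strongest reply is that SAP 10.4 does not present the search as the final classification. It calls the criteria an aid and provides for a medical-monitor review, which could apply the definition in SAP 4.6.2. That mitigates the gap without closing it. The review is optional, is framed as a review of preferred terms, and states no duration rule. In the systemic hypersensitivity row of the same table, by contrast, manual adjudication is mandatory.

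The objection on weight also stands. This is a single-arm study with descriptive safety analysis. Every affected event stays in the treatment-emergent AE tables, with its duration in the listings. AESIs, including ocular events of 4 weeks or more, still "must be reported within 24 hours of identification" under Protocol 10.4.3.

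The keratitis half is weaker than the conjunctivitis half. A wider search conceals nothing and may be deliberate. In the text read from the PDF, that row also crosses a page break with a missing figure, so there is a small doubt whether a qualifier was lost. The conjunctivitis/blepharitis row leaves little such doubt, because its label and its condition agree with each other.

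A reader might infer three stronger points that the documents do not support:

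- *That searching by preferred term departs from the protocol.* Protocol 11.4.4.1 expressly allows it: "Treatment-emergent AESIs (defined with a PT or a prespecified grouping)".
- *That the loss can be sized from the 10% conjunctivitis rate on the two-weekly regimen in Protocol 3.3.1.* That rate comes from adolescents with atopic dermatitis and covers conjunctivitis generally, not the non-serious, non-severe events of 4 weeks or more that the search misses.
- *That imputed end dates would corrupt a duration flag.* SAP 6.4 imputes AE end dates only as an intermediate step and keeps only the recorded date in the final dataset.

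**Conclusion.** The inconsistency is real and should be corrected before database lock. As written, the conjunctivitis/blepharitis category omits non-serious, non-severe events of at least 4 weeks, and the keratitis category includes non-serious, non-severe events of under 4 weeks. Neither matches SAP 4.6.2 or Protocol 10.4.3. The first is an error on the face of the text. The second is either an error or an undeclared choice.

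The consequence is limited to the descriptive AESI summaries and the time-to-first-AESI curves. It does not touch the primary endpoint, the overall AE tables or the reporting of AESIs to the sponsor, and the text does not support reading it as a suppressed safety signal. How many events are affected is unknown and could be none. The conclusion assumes that SAP 10.4 is programmed as written and that the optional review does not apply the duration rule.

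**What to change.** 1. In SAP 10.4, apply one condition to the conjunctivitis, blepharitis and keratitis rows: serious = yes, OR severity = severe, OR duration ≥28 days (4 × 7), with duration = end date − start date + 1. Use the recorded end date, in line with SAP 6.4. SAP 6.4 already covers incomplete start dates, so no separate start-date rule is needed.
2. Correct the conjunctivitis/blepharitis row label so that it includes the duration arm.
3. For events that are neither serious nor severe and whose duration cannot be established, require medical-monitor review before database lock. These are events with a partial or missing end date, and events ongoing at the last visit with under 28 days observed.
4. If an unfiltered keratitis search is intended, state this in SAP 4.6.2 and list it in SAP 1.2.3 as a departure from Protocol 10.4.3. Changing SAP 4.6.2 alone would create a new, undeclared mismatch with the protocol.

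The cost is a wording change to one table, one derived flag and a short manual review. No new data are needed. The AESI counts may change: possibly a few more under conjunctivitis/blepharitis and, if the filter is applied there, fewer under keratitis.
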